6.3. Measures to Minimize Bias: Randomization and Blinding

Stratified randomization will be done through IRT using the stratification factors described below. Stratified randomization will be performed separately for participants with FL and MZL.

Participants with FL will be stratified at the time of randomization for the following factors:

- POD24 (yes vs no)
- Refractoriness to prior anti-CD20 mAb therapy (yes vs no)
- The number of prior lines of therapy ($< 2 \text{ vs} \ge 2$).

Participants with MZL will be stratified at the time of randomization for the following factor:

• The number of prior lines of therapy ($< 2 \text{ vs} \ge 2$).

Further details of procedures regarding participant randomization and treatment assignment is provided in the Suvoda IRT Site User Manual.

Block size and block permutation algorithms are specified in a separate Randomization Plan. Blinded treatment will be used to reduce potential bias during data collection and evaluation of clinical endpoints. Details of tafasitamab/placebo treatment blinding will be outlined in the Pharmacy Manual. This is a double-blind study; therefore, participants, investigators, and the study team members will remain blinded to treatment assignment. The investigator will not be provided with randomization codes.

Data that may potentially unblind the treatment assignment (ie, study treatment concentrations) will be handled with special care to ensure that the integrity of the blind is maintained, and the potential for bias is minimized. This will include making special provisions such as segregating the data in question from view by the investigators, clinical team, or others as appropriate until the time of database lock and/or unblinding.

Participants, investigators, and the study team members will remain blinded to treatment assignment until the time of the primary analysis. Unblinding procedures and the control of the unblinded data are described in the IDMC charter. Examples of personnel who may be unblinded during the study are as follows:

- The IDMC and the biostatistician and statistical programmers from an independent statistical support group who are responsible for preparing interim tables, listings, and graphs for IDMC review.
- The sponsor's safety team in order to fulfill regulatory reporting requirements for SUSARs.
- In case of an urgent safety concern, the clinical study site personnel and the sponsor may be unblinded if treatment assignment information is needed to determine further actions to address the urgent safety concern (eg, life-threatening event, medication error such as an accidental overdose).

6.4. Study Treatment Compliance

Compliance with study treatment administration will be calculated by the sponsor based on study drug accountability and infusion records documented by the site staff and monitored by the sponsor/designee.

Participants should receive tafasitamab/placebo under direct supervision of clinical study site unblinded personnel. Each administration volume will be checked, and the vial code and volume per administration will be recorded in each participant's eCRF as well as in the source data. Unblinded data for tafasitamab will be captured in a separate eCRF database via the IRT system and will be monitored by an unblinded CRA. Refer to the Pharmacy Manual and Suvoda IRT Site User Manual for details.

The dosing of tafasitamab or placebo will be considered appropriate if the dose administered is $\geq 80\%$ to $\leq 120\%$ of the assigned dose per single infusion. Overdose treatment is described in Section 9.10.

Lenalidomide will be dispensed on Day 1 of each new treatment cycle. Participants will return all unused or empty lenalidomide blister packs to the clinical study site throughout the treatment period as instructed by the investigator, and keep a record of lenalidomide doses taken at home, which will be reviewed by clinical study site personnel on an ongoing basis. The clinical site personnel will document the amount of study drug received from and returned to the sponsor and dispensed to participants in accordance with local regulatory requirements. Throughout the course of the study, drug accountability records must be maintained. A participant will be considered compliant with the Protocol if the lenalidomide dose administered is $\geq 80\%$ to 100% of the assigned dosage. Overdose treatment is described in Section 9.10.

6.5. Dose Modifications

6.5.1. Tafasitamab/Placebo Dose Modifications

Dose reductions of tafasitamab/placebo are not permitted. Drug interruptions or discontinuation may occur in the case of severe IRRs, allergic reactions, infections, febrile neutropenia, or severe hematologic toxicity. Delaying the administration of tafasitamab/placebo is permitted for **no more than 2 days**. If the delay lasts more than 2 days, administration of tafasitamab/placebo must be skipped completely, and the next scheduled dose will be administered (eg, if an infusion is skipped on Day 8, the next dose will be administered on Day 15).

6.5.2. Criteria and Procedures for Dose Interruptions and Adjustments of Tafasitamab/Placebo

6.5.2.1. Management of Tafasitamab/Placebo Infusion-Related Reactions and Cytokine Release Syndrome

Infusion-related reactions will be defined according to the NCI CTCAE v5.0 definition of IRR and CRS (see Table 8).

Table 8: Definition of Infusion-Related Reactions and Cytokine Release Syndrome

Adverse Event	Grade 1	Grade 2	Grade 3	Grade 4
IRR	Mild transient reaction; infusion interruption not indicated; intervention not indicated	Therapy or infusion interruption indicated but responds promptly to symptomatic treatment (eg, antihistamines, NSAIDs, narcotics, IV fluids); prophylactic medications indicated for ≤ 24 hours	Prolonged (ie, not rapidly responsive to symptomatic medication, brief interruption of infusion, or both); recurrence of symptoms following initial improvement; hospitalization indicated for clinical sequelae	Life-threatening consequences; urgent intervention indicated
CRS	Fever with or without constitutional symptoms	Hypotension responding to fluids; hypoxia responding to $< 40\% O_2^a$	Hypotension managed with one pressor; hypoxia requiring $\geq 40\% \text{ O}_2^{\text{a}}$	Life-threatening consequences; urgent intervention indicated

NSAIDs = nonsteroidal anti-inflammatories.

Source: NCI CTCAE v5.0 (2017).

Note: An acute IRR may occur with an agent that causes cytokine release (eg, mAbs or other biological agents). Signs and symptoms usually develop during or shortly after drug infusion and generally resolve completely within 24 hours of completion of infusion. Signs/symptoms of an acute IRR may include (but are not limited to) the following: allergic reaction/hypersensitivity (including drug fever), arthralgia (joint pain), bronchospasm, cough, dizziness, dyspnea, fatigue (asthenia, lethargy, malaise), headache, hypertension, hypotension, myalgia, nausea, pruritus/itching, rash/desquamation, rigors/chills, sweating (diaphoresis), tachycardia, tumor pain (onset or exacerbation of tumor pain due to treatment), urticaria (hives, welts, wheals), and vomiting.

6.5.2.2. Interventions for Infusion-Related Reactions and Cytokine Release Syndrome

6.5.2.2.1. Grade 2 Infusion-Related Reactions, Grade 1 Cytokine Release Syndrome

The following should occur if a participant presents with a Grade 2 IRR or Grade 1 CRS:

- The infusion should be stopped immediately.
- The participant should receive appropriate treatment with an antihistamine and/or acetaminophen (paracetamol) or methylprednisolone (or equivalent) as clinically indicated.
- Once the symptoms have been resolved or reduced to Grade 1 (IRR) according to investigator assessment, the infusion can be continued at 50% of the last infusion rate. If, after 1 hour, the participant's symptoms do not return and vital signs are stable, the infusion rate may be increased every 30 minutes, as tolerated, to the baseline rate.

If a participant who developed a Grade 2 IRR or Grade 1 CRS receives further infusions of tafasitamab/placebo, then premedication should be given before all subsequent infusions of tafasitamab/placebo throughout the study.

^a Applied, for example, via breathing mask.

If a participant develops an additional episode, that is, a recurrent Grade 2 IRR or Grade 1 CRS, then the participant may receive further tafasitamab/placebo based on the investigator's decision, provided clinically appropriate precautions are undertaken. Premedication must be given before all subsequent infusions of tafasitamab/placebo.

If precluded from further tafasitamab/placebo administrations, the participant may continue treatment with rituximab and/or lenalidomide.

6.5.2.2.2. Grade 3 Infusion-Related Reactions, Grade 2 Cytokine Release Syndrome

The following should occur if a participant presents with a Grade 3 IRR or Grade 2 CRS:

- The infusion should be stopped immediately.
- Appropriate treatment with an antihistamine and/or acetaminophen (paracetamol) or methylprednisolone (or equivalent) and, if necessary, further medications (ie, epinephrine, bronchodilator).
- Only after the complete resolution of all symptoms and after having received appropriate prophylactic medication(s) as described above, the infusion may be resumed at 25% of the last infusion rate. If, after approximately 1 hour, the participant's symptoms do not return and vital signs are stable, the infusion rate may be increased every 30 minutes to a maximum of 50% of the baseline rate.
- If, after the resumption of the infusion, symptoms return (irrespective of grade), the infusion must be stopped immediately, and the infusion tubing disconnected from the participant.

Based on the investigator's decision, the participant may receive further tafasitamab/placebo provided clinically appropriate precautions are undertaken. If a participant who developed a Grade 3 IRR or Grade 2 CRS receives further infusions, then premedication will be given before all subsequent infusions of tafasitamab/placebo throughout the study.

If a participant develops another Grade 3 IRR or Grade 2 CRS, then the participant will be permanently discontinued from further tafasitamab/placebo administrations. If tafasitamab/placebo is discontinued, the participant may still continue to receive treatment with rituximab and lenalidomide.

6.5.2.2.3. Grade 4 Infusion-Related Reactions, Grade 3 to 4 Cytokine Release Syndrome

The following must occur if a participant presents with a Grade 4 infusion reaction or Grade 3 to 4 CRS:

- The infusion must be stopped immediately, and the infusion tubing disconnected from the participant.
- Appropriate treatment with an antihistamine and/or acetaminophen (paracetamol) or methylprednisolone (or equivalent) and, if necessary, further medications (ie, epinephrine, bronchodilator).
- The participant will be permanently discontinued from further tafasitamab/placebo administrations.

If tafasitamab/placebo is discontinued, the participant may continue treatment with rituximab and lenalidomide.

6.5.3. Criteria and Procedures for Dose Interruptions or Adjustments of Lenalidomide

Lenalidomide dose adjustments will be performed according to the label as described in Appendix B and in Section 6.5.5.

6.5.4. Criteria and Procedures for Dose Interruptions or Adjustments of Rituximab

Dose modifications of rituximab are not mandated unless clinically indicated as per the SmPC, the USPI, and applicable institutional guidelines (MabThera 2020, Rituxan 2020).

6.5.5. Toxicity Management Guidelines for Hematological Toxicities

In case of hematologic toxicities, tafasitamab/placebo, lenalidomide and/or rituximab treatment may need to be interrupted or discontinued according to the toxicity management guidelines provided in Table 9.

Delaying the tafasitamab/placebo dose or the rituximab dose is permitted for no more than
2 days (≤ 2 days). If a tafasitamab/placebo or rituximab infusion is delayed for 3 or more days
(≥ 3 days), then this infusion should be skipped and tafasitamab/placebo or rituximab treatment continued only at the next scheduled timepoint. Investigators may choose to follow their institution's standard of care for delayed dosing due to toxicity for lenalidomide and rituximab. This is acceptable and should be noted in the participant's medical record.

Dose reductions of tafasitamab/placebo or rituximab are not permitted. See Table 9 and Appendix A for guidance on dose adjustments for lenalidomide.

Table 9: Toxicity Management Guidelines for Hematological Toxicities

Adverse Eventa	Tafasitamab/Placebo	Lenalidomide	Rituximab
Thrombocytopenia Grade 3 (platelets < 50-25 G/L) with or without bleeding	 Interrupt tafasitamab/ placebo. Follow CBC at least every 7 days. If thrombocytopenia has resolved to ≤ Grade 2 (platelets ≥ 50 G/L), restart tafasitamab/ placebo at the same dose. Monitor as clinically indicated. 	 Interrupt lenalidomide. Follow CBC at least every 7 days. If thrombocytopenia has resolved to ≤ Grade 2 (platelets ≥ 50 G/L), restart lenalidomide at the next lower dose level (see Appendix B). Monitor as clinically indicated 	 Interrupt rituximab. Follow CBC at least every 7 days. If thrombocytopenia has resolved to ≤ Grade 2 (platelets ≥ 50 G/L), restart rituximab at the same dose. Monitor as clinically indicated.
Thrombocytopenia Grade 4 (platelets < 25 G/L)	 Interrupt tafasitamab/placebo. Follow CBC at least every 7 days. If thrombocytopenia has resolved to ≤ Grade 2 (platelets ≥ 50 G/L), restart tafasitamab/placebo at the same dose. Monitor as clinically indicated. 	 Interrupt lenalidomide Follow CBC at least every 7 days. If thrombocytopenia has resolved to ≤ Grade 2 (platelets ≥ 50 G/L), restart lenalidomide at the next lower dose level (see Appendix B). Monitor as clinically indicated 	 Interrupt rituximab. Follow CBC at least every 7 days. If thrombocytopenia has resolved to ≤ Grade 2 (platelets ≥ 50 G/L), restart rituximab at the same dose. Monitor as clinically indicated.
Thrombocytopenia Grade 3-4	 Interrupt VTE prophylaxis. Consider platelet transfusion Consider change of VTE promolecular weight heparin). VTE prophylaxis should be taking into account the indiv 	pphylaxis agent (eg, change an	lual risk/benefit profile by
Neutropenia Grade 3 (ANC < 1.0 G/L) sustained < 7 days	 Interrupt tafasitamab/placebo. Follow CBC at least every 7 days. Use growth factors (eg, G-CSF) and anti-microbial prophylaxis as per local guidelines. If neutropenia has resolved to ≤ Grade 2 (ANC ≥ 1.0 G/L), restart tafasitamab/placebo at the same dose. Monitor as clinically indicated. 	 Interrupt lenalidomide. Follow CBC at least every 7 days. Use growth factors (eg, G-CSF) and anti-microbial prophylaxis as per local guidelines. If neutropenia has resolved to ≤ Grade 2 (ANC ≥ 1.0 G/L), restart lenalidomide at the same dose. Monitor as clinically indicated. 	 Interrupt rituximab. Follow CBC at least every 7 days. Use growth factors (eg, G-CSF) and anti-microbial prophylaxis as per local guidelines. If neutropenia has resolved to ≤ Grade 2 (ANC ≥ 1.0 G/L), restart rituximab at the same dose. Monitor as clinically indicated.

Table 9: Toxicity Management Guidelines for Hematological Toxicities (Continued)

Adverse Eventa	Tafasitamab/Placebo	Lenalidomide	Rituximab
Neutropenia Grade 3 (ANC < 1.0 G/L) with a temperature of ≥ 38.5°C/ 101.3°F (febrile neutropenia)	 Interrupt tafasitamab/placebo. Follow CBC at least every 7 days. Use growth factors (eg, G-CSF) and antimicrobial prophylaxis as per local guidelines. If fever is resolving (< 38.0°C/100.4°F) and neutropenia has resolved to ≤ Grade 2 (ANC ≥ 1.0 G/L), restart tafasitamab/placebo at the same dose. Monitor as clinically indicated. 	 Interrupt lenalidomide. Follow CBC at least every 7 days. Use growth factors (eg, G-CSF) and anti-microbial prophylaxis as per local guidelines. If fever is resolving (< 38.0°C/100.4°F) and neutropenia has resolved to ≤ Grade 2 (ANC ≥ 1.0 G/L), restart lenalidomide at the next lower dose level (see Appendix B). Monitor as clinically indicated. 	 Interrupt rituximab. Follow CBC at least every 7 days. Use growth factors (eg, G-CSF) and anti-microbial prophylaxis as per local guidelines. If fever is resolving (< 38.0°C/100.4°F) and neutropenia has resolved to ≤ Grade 2 (ANC ≥ 1.0 G/L), restart rituximab at the same dose. Monitor as clinically indicated.
Neutropenia Grade 4 (ANC < 0.5 G/L) with or without a temperature of ≥ 38.5°C/101.3°F	 Interrupt tafasitamab/placebo. Follow CBC at least every 7 days. Use growth factors (eg, G-CSF) and anti-microbial prophylaxis as per local guidelines. If neutropenia has resolved to ≤ Grade 2 (ANC ≥ 1.0 G/L), restart tafasitamab/placebo at the same dose. Monitor as clinically indicated. 	 Interrupt lenalidomide. Follow CBC at least every 7 days. Use growth factors (eg, G-CSF) and anti-microbial prophylaxis as per local guidelines. If neutropenia has resolved to ≤ Grade 2 (ANC ≥ 1.0 G/L), restart lenalidomide at the next lower dose level (see Appendix B). Monitor as clinically indicated. 	 Interrupt rituximab. Follow CBC at least every 7 days. Use growth factors (eg, G-CSF) and anti-microbial prophylaxis as per local guidelines. If neutropenia has resolved to ≤ Grade 2 (ANC ≥ 1.0 G/L), restart rituximab at the same dose. Monitor as clinically indicated.

Table 9: Toxicity Management Guidelines for Hematological Toxicities (Continued)

Adverse Eventa	Tafasitamab/Placebo	Lenalidomide	Rituximab
Neutropenia Grade 3-4 sustained ≥ 7 days	 Interrupt tafasitamab/ placebo. Follow CBC at least every 7 days. Use growth factors (eg, G-CSF) and anti-microbial prophylaxis as per local guidelines. 	 Interrupt lenalidomide. Follow CBC at least every 7 days. Use growth factors (eg, G-CSF) and anti-microbial prophylaxis as per local guidelines. 	 Interrupt rituximab. Follow CBC at least every 7 days. Use growth factors (eg, G-CSF) and anti-microbial prophylaxis as per local guidelines.
	 If neutropenia has resolved to ≤ Grade 2 (ANC ≥ 1.0 G/L), restart tafasitamab/placebo at the same dose. Monitor as clinically indicated. 	 If neutropenia has resolved to ≤ Grade 2 (ANC ≥ 1.0 G/L), restart lenalidomide at the next lower dose level (see Appendix B). Monitor as clinically indicated. 	 If neutropenia has resolved to ≤ Grade 2 (ANC ≥ 1.0 G/L), restart rituximab at the same dose. Monitor as clinically indicated.

^a If, based on medical judgment, the treating physician considers a laboratory parameter change or AE not to be a study drug related toxicity, but to represent a natural fluctuation in or progression of the underlying disease, then it is at the physician's discretion and assessment of the individual risk/benefit ratio to determine whether the participant should be dosed. The decision and rationale behind the decision should be documented in the source data.

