8.3.5.1. Central Laboratory Testing for Safety

The measurement of all safety laboratory parameters (except pregnancy testing) as indicated in this Protocol will be performed centrally. Central laboratory tests will be performed according to Table 4. Laboratory results are required for determining participant eligibility for study enrollment and will be used for the primary statistical analysis of the study results.

During screening, it is permitted to repeat the laboratory assessment of serum chemistry and hematology parameters due to the variability of the parameters and their dependence on multitude of factors (eg, hydration, muscle mass). This is valid provided no safety concerns arise and that such laboratory results might have been caused by a transient, medically plausible event, which resolved spontaneously or as result of a medical intervention in the meantime (eg, dehydration, vomiting, imaging procedure with a contrast). This procedure and the rationale behind it must be explicitly documented in source data. Such repeated assessment (once only) of the concerned parameters will not be counted as "rescreening" for that participant.

Laboratory samples may be taken as defined in Table 4. Local laboratory results may be used for taking treatment or clinically related decisions, or for the immediate safety management of a study participant; in that situation, the site will be requested to send a sample to the central laboratory for confirmation of the result(s). The investigator or designee should review laboratory results before dosing so that the administration of the study drug(s) may be adjusted or interrupted if necessary.

The laboratory results will be kept in the participant's source documentation. Any clinically significant discrepancies will be evaluated on a case-by-case basis. All blood samples will be processed and handled according to standard laboratory procedures. The time of blood collection should be documented in the source data.

Clinical laboratory parameters assessed in this clinical study are displayed in Table 11 below.

Table 11: Required Laboratory Analytes

Serum Chemistries	Hematology	Urinalysis
ALT	Hemoglobin	Glucose
Albumin	Hematocrit	Ketone
Alkaline phosphatase	Platelet count	Occult blood
Amylase	WBC count including differentials	pН
AST		Protein
Bicarbonate/CO ₂ (may not be	Coagulation parameters:	Specific gravity
applicable in Japan)	aPTT	Urobilinogen
Bilirubin (total, direct, indirect)	D-dimer	
Calcium	PT	

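### Table 9 omits the fever condition for restarting treatment from the Grade 4 neutropenia row, although that row expressly covers febrile participants

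*Protocol*

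**What the plan says.** Table 9 in Protocol Section 6.5.5 has adjacent rows for Grade 3 neutropenia with a temperature of at least 38.5°C and for Grade 4 neutropenia.

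- **Grade 3 with fever.** The trigger is ANC below 1.0 G/L plus that temperature. The tafasitamab/placebo cell reads: "If fever is resolving (< 38.0°C/100.4°F) and neutropenia has resolved to ≤ Grade 2 (ANC ≥ 1.0 G/L), restart tafasitamab/placebo at the same dose". The lenalidomide and rituximab cells carry the same two conditions.
- **Grade 4.** The heading is "Neutropenia Grade 4 (ANC < 0.5 G/L) with or without a temperature of ≥ 38.5°C/101.3°F". All three cells restart once ANC is at least 1.0 G/L. Temperature is not mentioned.

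The text before the table presents it as guidance: treatment "may need to be interrupted or discontinued according to the toxicity management guidelines provided in Table 9". Section 6.5.5 also lets investigators follow institutional practice when delaying lenalidomide or rituximab for toxicity. For tafasitamab/placebo, Section 6.5.1 says: "Drug interruptions or discontinuation may occur in the case of severe IRRs, allergic reactions, infections, febrile neutropenia, or severe hematologic toxicity".

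**The concern.** The Grade 4 row names fever in its heading, so it does not leave febrile participants to the row above. Yet it drops the one written temperature condition for restart, and it does so for the deeper neutropenia. Elsewhere the table moves with severity: lenalidomide returns at the same dose after brief Grade 3 neutropenia and one level lower after febrile, Grade 4 or prolonged neutropenia. The fever condition runs the other way, and no reason is given.

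What is at stake is participant safety and uniform handling across sites. Section 2.3 identifies infections and neutropenic fever as the main treatment-related serious events, and says this three-drug combination is being tested for the first time. A site that applies the Grade 4 row by its label could restart three drugs in someone who is still febrile, while another site holds them.

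**Working it through.** The plan states no figure on this point, so the check is a comparison of text.

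**Step 1. The two rows, cell by cell (Section 6.5.5, Table 9).**

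| | Grade 3 with fever | Grade 4 |
|---|---|---|
| ANC trigger | < 1.0 G/L, no lower limit | < 0.5 G/L |
| Temperature in heading | ≥ 38.5°C | with or without ≥ 38.5°C |
| ANC needed to restart | ≥ 1.0 G/L | ≥ 1.0 G/L |
| Temperature needed to restart | < 38.0°C | none |
| Tafasitamab/placebo and rituximab | same dose | same dose |
| Lenalidomide | one level lower | one level lower |

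The temperature condition appears in 3 of 3 restart cells in the first row and 0 of 3 in the second. ANC threshold and restart dose are identical, so temperature is the only difference between the restart rules.

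**Step 2. Which row applies.** By label, ANC below 0.5 G/L belongs to the Grade 4 row. By number, it also satisfies the febrile row, because that row sets no ANC floor. The Grade 3 platelet row, by contrast, does state a lower limit (25 G/L). A febrile participant with ANC below 0.5 G/L can therefore meet both rows, and the table does not say which governs.

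**Step 3. Illustrative cases, each now at ANC 1.0 G/L.**

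- *A.* Nadir 0.6 with 39°C; temperature now 38.4°C. Only the febrile row applies: wait.
- *B.* Nadir 0.4 with 39°C; temperature stays at 38.8°C throughout recovery. Between 0.5 and 1.0 G/L this participant meets the febrile row, label included, so the < 38.0°C condition is triggered: wait.
- *C.* Nadir 0.4; temperature of 38.5°C or more only while ANC is below 0.5 G/L, then 38.0 to 38.4°C during recovery and now. The Grade 4 row by label says restart. The febrile row by its ANC number says wait.

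The gap is therefore clearest in case C, and likewise when fever is intermittent.

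**Step 4. Is a restart temperature set anywhere else?**

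- Section 6.5.1 permits interruption of tafasitamab/placebo for infection or febrile neutropenia; it gives no restart temperature.
- Institutional practice in Section 6.5.5 is optional, covers lenalidomide and rituximab only, and gives no temperature.
- Table 9, footnote a, leaves it to the physician "to determine whether the participant should be dosed", but only when the event is judged not drug related.
- Table 10 interrupts lenalidomide for other non-hematologic events of Grade 3 or higher until Grade 2 or lower, and continues both antibodies if clinically appropriate. Appendix B has a similar Grade 2 rule for related lenalidomide toxicity. Neither names a temperature.
- Section 8.3.5.1 says the investigator or designee "should review laboratory results before dosing so that the administration of the study drug(s) may be adjusted or interrupted if necessary". That concerns laboratory values.

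No restart temperature for the Grade 4 row was found.

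**The case against.** The strongest reply is that the febrile row already protects these participants. It is labelled as febrile neutropenia, it has no ANC floor, and anyone still at 38.5°C or above while ANC climbs back through Grade 3 meets it outright. This stands for case B, and it rules out a tempting stronger reading: that the table tells sites to restart every febrile Grade 4 participant as soon as ANC recovers. It does not settle case C, because that row is labelled Grade 3 while the next row expressly claims Grade 4 with fever. At best, two rows with different rules cover the same person.

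Second, every drug has written support for holding: Section 6.5.1 for tafasitamab/placebo, and institutional practice in Section 6.5.5 for lenalidomide and rituximab. Table 10 and Appendix B add resolution criteria for Grade 3 or higher events. This also stands: no site is obliged to dose a febrile participant. But permission to hold is not a rule for when to resume.

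Third, the row headed "Neutropenia Grade 3-4 sustained ≥ 7 days" is also silent on fever. A febrile participant there meets the febrile row as well, and satisfying both means using the stricter rule. That overlap is secondary, and the point does not rest on it.

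**Conclusion.** Wrong as written: a minor inconsistency in a safety rule. Three restart cells expressly cover fever without a fever condition, while the three matching cells in the row above have one. The conclusion rests on reading the Grade 4 row by its label, and on no other section supplying a restart temperature.

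The number affected is unknown. A reader might be tempted to scale from the febrile neutropenia rates in Section 2.1.4.6 (12.3% overall; 6.2% for serious events of Grade 3 or higher). The documents do not support that. Those rates come from R/R DLBCL treated with tafasitamab plus lenalidomide without rituximab, they cannot be carried over to the placebo group, and they count all febrile neutropenia rather than Grade 4 episodes in which ANC recovers before fever settles. No effect on endpoints, power or error rate is claimed.

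**What to change.** In the three Grade 4 restart cells, keep the requirement for ANC of at least 1.0 G/L and add that, if the participant is febrile, the temperature must also have come down below 38.0°C (100.4°F). The doses at restart stay as they are. This can go into the next amendment, with a memo to sites.

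The cost is small. Section 8.3.3 already requires vital signs, including body temperature, before each tafasitamab/placebo infusion. Lenalidomide is taken at home (Section 6.4), and from Cycle 4 infusions fall on Days 1 and 15, which is 15 − 1 = 14 days apart. A lenalidomide restart between visits may therefore need an extra temperature reading. It can be taken when the recovery blood count is drawn, since Table 9 already says: "Follow CBC at least every 7 days".

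The downside is an occasional delayed or skipped dose, because an antibody infusion delayed by 3 days or more is skipped. From the schedule in Section 6.1:

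- Tafasitamab/placebo: 3 × 4 + 9 × 2 = 30 infusions, so one skipped is 1/30 = 3.3%.
- Rituximab: 4 + 4 = 8 infusions, so one skipped is 1/8 = 12.5%.

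The protocol already accepts this cost in the Grade 3 febrile row.
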